### 6.6.2 BGB324 dose modification for QTc

Treatment with BGB324 produces QTc prolongation. In order to reduce the risk of QTc prolongation, all efforts should be made to maintain the patient's serum potassium levels at  $>4$  mmol/L during treatment with BGB324 and for 2 weeks following completion of therapy (at an unscheduled visit, if required). Serum calcium and magnesium should be measured and reasonable efforts made to maintain at normal levels throughout treatment. Patients with an average QTc of  $\geq 480$  ms should be closely monitored until the QTc falls below 480 ms; electrolytes should be measured and corrected as necessary.

If a patient experiences QTc prolongation, BGB324 dosing should be reduced as outlined in [Table 13](#). **Treatment with BGB324 should be permanently discontinued in the presence of ventricular arrhythmia.**

**Table 13: Dose modification of BGB324 for QTc Prolongation**

QTcF	Recommended BGB324 Dose Modification
Grade 1 (450-480 ms)	
Any occurrence	No dose modification required
Grade 2 (481-500 ms) - on two consecutive occasions per protocol assessments or investigator's judgement	
1 st occurrence	Interrupt treatment with BGB324: i) if QTcF reduces to $\leq$ Grade 1 by 14 days from initial recording, restart BGB324 at a reduced dose of 100mg or discontinue if no further dose reduction is possible. ii) if QTcF does not reduce to $\leq$ Grade 1 by 14 days from initial recording, discontinue BGB324 permanently.
$\geq$ 2 nd occurrence (following a previous dose reduction for QTcF)	Discontinue BGB324 permanently.
$\geq$ Grade 3 ( $\geq$ 501 ms)	
1 st occurrence	Interrupt treatment with BGB324: - if QTcF reduces to $\leq$ Grade 1 by 14 days from initial recording, restart BGB324 at a reduced dose of 100mg or discontinue treatment if dose reduction is not possible - if QTcF does not reduce to $\leq$ Grade 1, discontinue BGB324 permanently.
2 nd occurrence	Discontinue BGB324 permanently
Ventricular arrhythmia	
1 st occurrence	Discontinue BGB324 permanently
Notes:	
• Serum calcium, magnesium and potassium should be measured regularly whilst receiving BGB324; all abnormal results should be corrected	
• The mean QTcF value from triplicate ECG readings should be used when considering dose modification	

QTcF	Recommended BGB324 Dose Modification
	

• Treatment interruption for BGB324-related toxicity should be limited to 14 days

• Dose reduction below 100 mg daily is not possible (a single capsule contains 100 mg BGB324)

• Patients being considered for dose reduction or permanent discontinuation of BGB324 may be discussed with the Medical Monitor

• Patients require an ECG twice weekly for the first 2 weeks after recommencing BGB324 following an interruption (see Section 5.3.9)

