- Alternatively, 2 core needle (fresh tumor) biopsies or a single newly obtained excisional biopsy sample can be submitted (processed into one FFPE block), together with either an archival (FFPE) tumor tissue block or a minimum of 10 unstained slides each 5 $\mu$ m cut from the archival tumor sample block. The unstained slides must arrive at the testing laboratory within 14 days. In this option, an archival FFPE block is strongly preferred over unstained slides cut from an archival FFPE block.

Archival blocks must be clearly labelled as archival.

Slides cut from an archival tissue block must be clearly marked as having come from an archival block.

Finally, where patients also have (additional) archived biopsy material which is suitable for additional (such as exploratory) biomarker assessment a sample of this material (either as an archival FFPE block or slides cut (and paraffin dipped) from the archival block) can also be prepared for study biomarker assessment. The patient will be offered a separate optional patient consent to enable this 'archival biomarker tumor sample' to be submitted.

The first dose of study drug must be administered within 4 weeks of commencing the Screening assessments. Tumor imaging by computed tomography (CT) or magnetic resonance imaging (MRI) of the chest, abdomen and pelvis is required during the Screening period. X-ray scans can be used where appropriate (for example, for symptomatic sites that are negative on a bone scan). All patients should undergo a bone scan and a brain scan in the 6 weeks prior to starting treatment.

Recording of AEs and concomitant medications, plus laboratory screens including electrocardiographs (ECGs) will be performed at each study visit. During Cycle 1, patients will have study visits on Days 1, 2, 3 and 4, then on Days 8 and 15. From Cycle 2, Day 1, study visits will be reduced to every 3 weeks.

ECG assessments will be performed in triplicate at pre-dose and 6 hours after the BGB324 dose on Day 1, Cycle 1 and then repeated pre-BGB324 dose on Days 2, 3 and 4 (Cycle 1) and then at every visit thereafter.

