**General instructions:**

- Informed Consent must be obtained using the current version of the PIS/ICF prior to commencing Screening.
- From C2 onwards a tolerance window of +/- 3 days is permitted. Other tolerance windows for specific study assessments are described in the footnotes below.
- On dosing days, assessments should be performed prior to dosing unless specified otherwise.
- (X) denotes an optional sample; or a sample which is not taken at every cycle; or the particular assessment is 'if applicable'; X denotes a study visit with multiple samples. Please refer to Footnotes.
- Additional assessments may be carried out at any point in the study where clinically indicated.

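### Table 13's Grade 2 QTcF row: on the scheduled-ECG route from Cycle 2, a 14-day recovery limit counted from the first ECG has passed before BGB324 is interrupted, and the start of that clock is undefined

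*Protocol*

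**What the plan says.** Section 6.6.2 and Table 13 of the protocol govern BGB324 dosing when QTcF is prolonged. The relevant provisions are these.

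- **Grade 2 trigger (481-500 ms).** The row applies when the value is seen "on two consecutive occasions per protocol assessments", or on the investigator's judgement.
- **Grade 2 consequence, first occurrence.** BGB324 is interrupted. Item i allows restart at the reduced dose, where a reduction is still possible, if QTcF is back to Grade 1 or less within 14 days. Item ii covers failure to recover "by 14 days from initial recording, discontinue BGB324 permanently".
- **Grade 3 or higher (501 ms or more).** Interruption follows the first occurrence. The restart condition uses the same 14 days from the same undefined starting point.
- **Table note.** "Treatment interruption for BGB324-related toxicity should be limited to 14 days". This limits the length of the interruption, which is a different interval.
- **Monitoring text in Section 6.6.2.** Patients with an average QTc of 480 ms or more "should be closely monitored until the QTc falls below 480 ms". No ECG interval is given.

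The ECG timetable is in the synopsis under Study Procedures and Assessments. ECGs are taken on Days 1 to 4 of Cycle 1 "and then at every visit thereafter". Cycle 1 also has visits on Days 8 and 15. After that, "From Cycle 2, Day 1, study visits will be reduced to every 3 weeks". The general instructions to Tables 4 and 5 add: "From C2 onwards a tolerance window of +/- 3 days is permitted".

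**The concern.** A rule that needs two recordings but counts its recovery period from the *initial* one uses up part of that period while waiting for the second. If the wait exceeds 14 days, the recovery test has been failed before the action it is meant to assess has begun. From Cycle 2 the routine schedule produces such a wait.

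Section 6.6.2 itself states that BGB324 produces QTc prolongation, and one of the two outcomes is irreversible. For a patient whose dose can still be reduced, one site could restart BGB324 and another could stop it for good on identical ECGs, depending on how each reads the clock. A patient who stops BGB324 may continue on pembrolizumab alone (Section 4.2) and stays evaluable after one combination dose (Sections 3.5 and 8.4). Different readings would therefore change how much combination exposure lies behind the response rate. They could also change the permanent-discontinuation rate that the Data Review Committee considers under Sections 4.1 and 8.2.1.

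**Working it through.** This is calendar arithmetic. The protocol states no derived figure to reproduce; its only stated number here is the 14-day limit.

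**Inputs**
- Recovery limit: 14 days from the initial recording (Table 13).
- Cycle 1 ECG days: 1, 2, 3, 4, 8 and 15 (synopsis). They are taken at their nominal days, since the general instructions grant the window from Cycle 2.
- From Cycle 2: one ECG per visit, every 21 days, with a window of 3 days either side of each visit.
- Reading tested: the clock starts at the first of the two qualifying ECGs, and both are scheduled ECGs.

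**Formulas**
- Gap range = nominal gap minus or plus the sum of the two visits' windows.
- Days left when the second ECG is read = 14 minus the gap.

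From Cycle 2 the shortest gap is 21 − (3 + 3) = 15 days and the longest is 21 + (3 + 3) = 27 days. Days left are 14 − 21 = −7 nominally, 14 − 15 = −1 at best and 14 − 27 = −13 at worst. For Cycle 1 Day 15 to Cycle 2 Day 1 only the second visit has a window, so the gap is 7 − 3 = 4 to 7 + 3 = 10 days.

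| Pair of scheduled ECGs | Gap, days (range) | Days left of 14 (range) |
|---|---|---|
| Cycle 1, Days 1-2, 2-3, 3-4 | 1 | 13 |
| Cycle 1, Day 4 to Day 8 | 4 | 10 |
| Cycle 1, Day 8 to Day 15 | 7 | 7 |
| Cycle 1 Day 15 to Cycle 2 Day 1 | 7 (4 to 10) | 7 (4 to 10) |
| Cycle 2 Day 1 to Cycle 3 Day 1, and each later pair | 21 (15 to 27) | −7 (−13 to −1) |

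From Cycle 2 even the shortest permitted gap exceeds 14 days. QTcF is by definition still Grade 2 at the second ECG, so on this reading item i cannot be met and item ii applies.

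**Other readings**
- *Clock starts at the ECG that completes the criterion.* All 14 days are available in every cycle, and the recovery clock agrees with the interruption limit in the table note.
- *Grade 3 row.* Action follows the first occurrence, so the initial recording and the start of the interruption coincide and 14 − 0 = 14 days remain.
- *Two clocks in the Grade 2 row.* If the recovery clock starts at the first ECG, it and the interruption limit differ by the gap between the ECGs, in Cycle 1 as well: from 1 day up to 10 days there.

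**Does any other text set the time of the second ECG?** Section 5.3.9 and the notes to Table 13 require ECGs twice weekly for 2 weeks, but only after BGB324 is restarted. The close-monitoring sentence gives no interval. The general instructions permit extra assessments without requiring them.

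**The case against.** The strongest reply is that the protocol gives sites several ways round the conflict.

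- The row can also be triggered by investigator's judgement, so two scheduled ECGs are not the only route. **This stands.** A reader might infer that the rule fires only after two scheduled ECGs; the row heading says otherwise.
- Every Grade 2 patient is at 480 ms or more and so falls under the close-monitoring sentence. Waiting three weeks is hard to call close monitoring, and clinically indicated ECGs are allowed. From Cycle 2 the Grade 3 row also needs an off-schedule ECG to document recovery by Day 14. **This stands as an escape route.** But no interval is set, and nothing says a monitoring ECG counts as one of the two occasions.
- *Initial recording* could mean the ECG that triggers action, as it does in the Grade 3 row, and the conflict then disappears. **This stands as a possible reading.** In a rule that needs two recordings, the first is at least as natural, and the protocol does not choose.
- The row is headed as a recommendation, and dose reduction or discontinuation may be discussed with the Medical Monitor. **This softens the consequence** but does not settle the wording.

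Three stronger inferences are tempting and not supported:
- *Milder prolongation always leads to the harsher outcome.* This follows only on the scheduled route from Cycle 2 with the clock at the first ECG.
- *No interruption rule covers the patient between visits.* Investigator's judgement, the rule for 501 ms or more and the ventricular-arrhythmia rule all apply in that interval.
- *The run-in thresholds would be distorted.* Section 8.2.1 (4 or more of 6 patients; 5 or more of 12) pools BGB324 reductions with permanent discontinuations. Restart at a reduced dose and permanent stop each count once, so the pooled count does not change. With a minimum follow-up of 6 weeks, the only affected scheduled pair is Day 22 to Day 43, at the very end of that period.

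**Conclusion.** The point holds in a limited form. On the scheduled-ECG route from Cycle 2, with the clock at the first ECG, the recovery limit expires 1 to 13 days (nominally 7) before the interruption begins, and the restart branch is unreachable. This rests on two assumptions: both qualifying ECGs are scheduled ones, and the undefined starting point is the first of them. If either fails, the restart branch may be reachable, so the outcome depends on each site's interpretation. In Cycle 1, 4 to 13 days remain and the limit does not expire first.

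The separately considered permanent-discontinuation rate and exposure to the combination could be affected; the pooled run-in count and the response-rate denominator are not. The documents do not allow an estimate of how many patients would be involved. A reader might take this as a defect that must be corrected before the trial can proceed. The escape routes and the Medical Monitor note do not support that. It is a wording amendment that should be made.

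**What to change.** Reconcile five elements so that they can all be met together and are read the same way at every site:

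1. the Grade 2 trigger in Table 13, including which ECGs count as the two occasions;
2. the event that starts the 14-day recovery clock, with *initial recording* defined once for both the Grade 2 and Grade 3 rows;
3. the 14-day limit on interruption in the table notes and Section 6.6.1, and its relation to the recovery clock;
4. the ECG schedule from Cycle 2 in Tables 4 and 5 and Section 5.3.9;
5. the close-monitoring sentence in Section 6.6.2, stating whether and how it bears on the second occasion.

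Which element changes is the sponsor's clinical decision; this review does not favour any of the readings. The cost is a wording change to one table, its notes and one paragraph at the next amendment, with a memo to sites. Sample size, decision rules and analysis sets are untouched.

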### 6.6.3 Pembrolizumab dose modifications

Adverse events (both non-serious and serious) associated with pembrolizumab exposure may represent an immunologic etiology. These AEs may occur shortly after the first dose or several months after the last dose of treatment. Pembrolizumab must be withheld for drug-related toxicities and severe or life-threatening AEs as per [Table 14](#) below. See [Section 6.11](#) for supportive care guidelines, including use of corticosteroids.

Table 14: Dose modification guidelines for pembrolizumab drug-related adverse events

Toxicity	Hold Treatment For Grade	Timing for Restarting Treatment	Treatment Discontinuation
Diarrhea/Colitis	2-3	Toxicity resolves to Grade 0-1	Toxicity does not resolve within 12 weeks of last dose or inability to reduce corticosteroid to 10 mg or less of prednisone or equivalent per day within 12 weeks
	4	Permanently discontinue	Permanently discontinue
AST, ALT, or Increased Bilirubin	2	Toxicity resolves to Grade 0-1	Toxicity does not resolve within 12 weeks of last dose
	3-4	Permanently discontinue (see exception below) a	Permanently discontinue
Type 1 diabetes mellitus (if new onset) or Hyperglycemia	T1DM or 3-4	Hold pembrolizumab for new onset Type 1 diabetes mellitus or Grade 3-4 hyperglycemia associated with evidence of beta cell failure	Resume pembrolizumab when patients are clinically and metabolically stable
Hypophysitis	2-4	Toxicity resolves to Grade 0-1. Therapy with pembrolizumab can be continued while endocrine replacement therapy is instituted	Toxicity does not resolve within 12 weeks of last dose or inability to reduce corticosteroid to 10 mg or less of prednisone or equivalent per day within 12 weeks
Hyperthyroidism	3	Toxicity resolves to Grade 0-1	Toxicity does not resolve within 12 weeks of last dose or inability to reduce corticosteroid to 10 mg or less of prednisone or equivalent per day within 12 weeks
	4	Permanently discontinue	Permanently discontinue
Hypothyroidism		Therapy with pembrolizumab can be continued while thyroid replacement therapy is instituted	Therapy with pembrolizumab can be continued while thyroid replacement therapy is instituted
Infusion Reaction	2 b	Toxicity resolves to Grade 0-1	Permanently discontinue if toxicity develops despite adequate premedication
	3-4	Permanently discontinue	Permanently discontinue
Pneumonitis	2	Toxicity resolves to Grade 0-1	Toxicity does not resolve within 12 weeks of last dose or inability to reduce corticosteroid to 10 mg or less of prednisone or equivalent per day within 12 weeks
	3-4 or Recurrent 2	Permanently discontinue	Permanently discontinue

Toxicity	Hold Treatment For Grade	Timing for Restarting Treatment	Treatment Discontinuation
Renal Failure or Nephritis	2	Toxicity resolves to Grade 0-1	Toxicity does not resolve within 12 weeks of last dose or inability to reduce corticosteroid to 10 mg or less of prednisone or equivalent per day within 12 weeks
	3-4	Permanently discontinue	Permanently discontinue
All Other Drug-Related Toxicity c	3 or Severe	Toxicity resolves to Grade 0-1	Toxicity does not resolve within 12 weeks of last dose or inability to reduce corticosteroid to 10 mg or less of prednisone or equivalent per day within 12 weeks
	4	Permanently discontinue	Permanently discontinue

**Note: Permanently discontinue for any severe or Grade 3 (Grade 2 for pneumonitis) drug-related AE that recurs or any life-threatening event.**

a For patients with liver metastasis who begin treatment with Grade 2 AST or ALT, if AST or ALT increases by greater than or equal to 50% relative to baseline and lasts for at least 1 week then patients should be discontinued.

b If symptoms resolve within one hour of stopping drug infusion, the infusion may be restarted at 50% of the original infusion rate (e.g., from 100 mL/hr to 50 mL/hr). Otherwise dosing will be held until symptoms resolve and the subject should be premedicated for the next scheduled dose; Refer to [Section 6.12, Table 18 – Infusion Treatment Guidelines for further management details](#).

c Patients with intolerable or persistent Grade 2 drug-related AE may hold study medication at physician discretion. Permanently discontinue study drug for persistent Grade 2 adverse reactions for which treatment with study drug has been held, that do not recover to Grade 0-1 within 12 weeks of the last dose.

Dosing interruptions are permitted in the case of medical / surgical events or logistical reasons not related to study therapy (e.g., elective surgery, unrelated medical events, patient vacation, and/or holidays). Patients should be placed back on study therapy within 3 weeks of the scheduled interruption, unless otherwise discussed with the Sponsor. The reason for interruption should be documented in the patient's study record.

#### 6.6.4 Dose modifications for BGB324 and pembrolizumab for overlapping toxicities

Three toxicities are identified as potentially overlapping with both BGB324 and pembrolizumab: diarrhea, rash (including dermatitis, pruritus) and renal toxicity (renal failure, serum creatinine elevation, nephritis).

See also, Supportive Care Guidelines for Pembrolizumab – [Section 6.11](#).

##### 6.6.4.1 Dose modifications for diarrhea

Patients may continue with baseline anti-diarrheal medications throughout treatment with pembrolizumab. If a patient experiences an increase in diarrheal symptoms after starting BGB324 they may increase the dose of anti-diarrheal medication such as loperamide during the first week of treatment only. Starting treatment with loperamide is also acceptable during this period. Thereafter any increased diarrheal symptoms should be reported to the investigator immediately and further medication should not be given. See [Table 15](#).

**Table 15: Pembrolizumab and BGB324 Dose Modification for Diarrhea**

Diarrhea with onset in the 2 nd cycle or later cycle	Pembrolizumab	BGB324
Grade 2-3	Withhold for up to 12 weeks of last dose 
 
• If resolved to Grade 0 or 1, restart pembrolizumab
 
• Permanently discontinue if not resolved to grade 0 or 1, or, there is an inability to reduce corticosteroid to <math>\leq 10</math> mg (prednisone or equivalent) per day
 
	Withhold for up to 14 days 
 
• If resolved to grade 0 or 1, restart BGB324 at 100 mg qd
 
• Permanently discontinue if not resolved to grade 0 or 1
 

Grade 4	Permanently discontinue	Permanently discontinue

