#### 6.6.4.3 Dose modifications for renal toxicity (renal failure, serum creatinine elevation, nephritis) – [Table 17](#)

**Table 17: Pembrolizumab and BGB324 Dose Modification for Renal Toxicity**

Renal failure, serum creatinine elevation, nephritis – onset during any cycle	Pembrolizumab	BGB324
Grade 2	Withhold for up to 12 weeks of last dose 
 
• If resolved to grade 0 or 1, restart pembrolizumab
 
• Permanently discontinue if not resolved to grade 0 or 1, or, there is an inability to reduce corticosteroid to <math>\leq 10</math> mg (prednisone or equivalent) per day
 
	Withhold for up to 14 days 
 
• If resolved to grade 0 or 1, restart at 100 mg qd
 
• Permanently discontinue if not resolved to grade 0 or 1
 

Grade 3	Permanently discontinue	Withhold for up to 14 days 
 
• If resolved to grade 0, 1 or tolerable grade 2, restart at 100 mg qd
 
• Permanently discontinue if not resolved to grade 0, 1 or tolerable grade 2
 

Grade 4	Permanently discontinue	Permanently discontinue

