## 6.8 Permitted and Restricted Concomitant Medications

In general, medications or vaccinations specifically prohibited in the exclusion criteria are not allowed during the ongoing trial. Treatment with antacids, proton pump inhibitors and histamine receptor 2 inhibitors can be initiated as rescue therapy after patients have been receiving BGB324 for one week, provided they are taken in the evening.

If there is a clinical indication for any medication or vaccination specifically prohibited during the trial, discontinuation from trial therapy or vaccination may be required. The investigator should discuss any questions regarding this with the Sponsor Clinical Director. The final decision on any supportive therapy or vaccination rests with the investigator and/or the patient's primary physician. However, the decision to continue the patient on trial therapy or vaccination schedule (see [Section 6.10](#)) requires the mutual agreement of the investigator, the Sponsor and the patient.

Patients should not receive BGB324 during periods of systemic corticosteroid treatment. If a patient requires treatment with systemic corticosteroids, BGB324 should be interrupted immediately. Treatment with BGB324 may be restarted upon completion of systemic corticosteroid therapy. BGB324 may be continued at the appropriate dosage during periods of topical and inhaled corticosteroid therapy.

Hormonal contraception for female breast cancer patients is contraindicated.

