## 6.11 Supportive Care Guidelines for Pembrolizumab

Patients should receive appropriate supportive care measures as deemed necessary by the treating investigator. Suggested supportive care measures for the management of AEs with potential immunologic etiology are outlined below. Where appropriate, these guidelines include the use of oral or intravenous treatment with corticosteroids as well as additional anti-inflammatory agents if symptoms do not improve with administration of corticosteroids. Patients receiving oral or intravenous corticosteroids must interrupt treatment with BGB324 throughout the duration of therapy.

Note that several courses of steroid tapering may be necessary as symptoms may worsen when the steroid dose is decreased. For each disorder, attempts should be made to rule out other causes such as metastatic disease or bacterial or viral infection, which might require additional supportive care. The treatment guidelines are intended to be applied when the investigator determines the events to be related to pembrolizumab.

Note: If after the evaluation the event is determined not to be related, the investigator does not need to follow the treatment guidance (as outlined below). Refer to [Section 6.6](#) for dose modification.

It may be necessary to perform conditional procedures such as bronchoscopy, endoscopy, or skin photography as part of evaluation of the event.

- **Pneumonitis:**

- For **Grade 2 events**, treat with systemic corticosteroids. When symptoms improve to Grade 1 or less, steroid taper should be started and continued over no less than 4 weeks.
- For **Grade 3-4 events**, immediately treat with i.v. steroids. Administer additional anti-inflammatory measures, as needed.
- Add prophylactic antibiotics for opportunistic infections in the case of prolonged steroid administration.
- **Diarrhea/Colitis:**  
Patients should be carefully monitored for signs and symptoms of enterocolitis (such as diarrhea, abdominal pain, blood or mucus in stool, with or without fever) and of bowel perforation (such as peritoneal signs and ileus).
  - All patients who experience diarrhea/colitis should be advised to drink liberal quantities of clear fluids. If sufficient oral fluid intake is not feasible, fluid and electrolytes should be substituted via i.v. infusion. For Grade 2 or higher diarrhea, consider GI consultation and endoscopy to confirm or rule out colitis.
  - For **Grade 2 diarrhea/colitis** administer oral corticosteroids.

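### For diarrhea and renal events treated with systemic steroids, the 14-day BGB324 hold in Tables 15 and 17 is too short for the steroid bar in Sections 6.8 and 6.11, and no passage says how the two rules combine

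*Protocol*

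**What the plan says.** Section 6.6 sends diarrhea, rash and renal toxicity to Section 6.6.4, so Tables 15 to 17 are where a site looks for these events.

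- **Table 15, diarrhea Grade 2-3, onset in cycle 2 or later.** BGB324 is withheld for up to 14 days, then: "If resolved to grade 0 or 1, restart BGB324 at 100 mg qd". It is stopped permanently if the event has not resolved.
- **Table 17, renal Grade 2.** Same 14-day hold, then: "If resolved to grade 0 or 1, restart at 100 mg qd".
- **Table 17, renal Grade 3.** Same 14-day hold, with a wider restart condition: "If resolved to grade 0, 1 or tolerable grade 2, restart at 100 mg qd".
- **Pembrolizumab column, diarrhea Grade 2-3 and renal Grade 2.** The hold may run up to 12 weeks from the last dose. One ground for stopping is that "there is an inability to reduce corticosteroid to" 10 mg or less of prednisone (or equivalent) per day.

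The steroid rules stand elsewhere.

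- **Section 6.8:** "Patients should not receive BGB324 during periods of systemic corticosteroid treatment". It continues: "Treatment with BGB324 may be restarted upon completion of systemic corticosteroid therapy".
- **Section 6.11:** "Patients receiving oral or intravenous corticosteroids must interrupt treatment with BGB324 throughout the duration of therapy". For diarrhea/colitis and for renal failure or nephritis of Grade 2 or higher, it suggests corticosteroids when the investigator attributes the event to pembrolizumab. The taper begins at Grade 1 or less and runs for at least four weeks.

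Section 6.6.4 points the reader to Section 6.11 ("See also, Supportive Care Guidelines for Pembrolizumab"), without saying how the two fit together.

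**The concern.** In these rows, reaching Grade 1 or less triggers two things. Under the tables it restarts BGB324. Under Section 6.11 it starts a steroid taper of four weeks or more, during which BGB324 is barred. The tables foresee steroid use, since the pembrolizumab column mentions it, but the neighbouring BGB324 entries do not, although BGB324 has the stricter steroid rule.

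Two sites could handle the same event differently. One that follows the BGB324 column literally would give BGB324 alongside systemic steroids, which Section 6.8 prohibits. One that follows Sections 6.8 and 6.11 would overrun the 14-day hold and would have to guess whether BGB324 may still be resumed.

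The bar has a stated background. Section 1.3.2 reports severe toxicity in 6 of 7 mice after five days of BGB324 with high-dose prednisolone, with the mechanism still under investigation. That section describes the steroid dose as 20-fold a typical high clinical dose, and the BGB324 dose as 6-fold the maximum human exposure. The mouse result shows why the instruction should be clear. It does not measure the risk created by the table wording.

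**Working it through.** The plan gives no figure of its own to reproduce. The check is a day count.

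**Inputs**
- Maximum BGB324 hold: 14 days (Tables 15 and 17).
- Minimum taper: 4 weeks = 28 days, starting at Grade 1 or less (Section 6.11, diarrhea/colitis and renal entries).
- BGB324 barred until systemic steroids are complete (Sections 6.8 and 6.11).
- r = day of the hold on which the event reaches Grade 1 or less. The tables allow r up to 14. Because the hold is triggered at Grade 2 or above, r = 0 is only a formal limit, and r is greater than 0 in practice.

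**Formula.** If the taper starts on day r, steroids end no earlier than day r + 28, so a hold that complies with Sections 6.8 and 6.11 lasts at least r + 28 days. The excess over the stated hold is (r + 28) − 14 = r + 14 days.

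| Resolution on day r | Minimum compliant hold | Excess over 14 days | Ratio to 14 days |
|---|---|---|---|
| 0 (formal limit) | 28 | 14 | 2.0 |
| 7 | 35 | 21 | 2.5 |
| 10 | 38 | 24 | 2.7 |
| 14 | 42 | 28 | 3.0 |

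For any r above 0 the minimum compliant hold exceeds 28 days. A taper longer than four weeks lengthens it further.

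**Literal table restart.** A restart at Grade 0-1 coincides with the start of the taper, so it overlaps at least 28 once-daily BGB324 doses with steroids. For renal Grade 3, a restart at tolerable Grade 2 comes before the taper can begin, and the days until Grade 1 are added. This is the result of applying the column alone. It presupposes that Sections 6.8 and 6.11 are overlooked.

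**Where no conflict arises.** Events managed without systemic steroids can meet the 14-day hold. Table 16 (rash) has the same 14-day structure, but Section 6.11 gives no steroid taper for rash, so the count does not apply there.

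**The case against.** The strongest reply is that the protocol already prevents co-administration. Section 6.8 is a trial-wide rule, Section 6.11 repeats it in mandatory terms, and Section 6.6.4 refers to Section 6.11 just before the tables. A general concomitant-medication rule need not be repeated in every dosing table, so the steroid bar can be read as an added condition on the table restart. This stands. A reader might infer that the protocol directs sites to give BGB324 with steroids; read as a whole, it does not.

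A second reply concerns stopping. A reader might infer that the 14-day limit forces BGB324 to be discontinued in a patient who has recovered but is still tapering. The text does not say so: both tables discontinue BGB324 when the event has not resolved, not on duration alone. Section 6.6.1 ties the 14 days to resolution of toxicity. Section 3.5 lists steroid interruptions apart from toxicity delays. Section 3.3 lists a delay beyond 14 days as a reason to stop where re-introduction is not considered suitable, which implies that it sometimes is. Wrongful discontinuation is therefore possible but not directed.

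A third reply is that Section 6.11 offers suggested measures, only for events attributed to pembrolizumab, so a four-week taper does not follow every event in these tables. That is right, and it limits the point to such events.

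One gap remains. Even with the bar read as an added condition, the resulting hold exceeds the stated 14 days. Sections 3.3, 3.5 and 6.6.1 hint at the intent, but none says whether the 14-day limit runs during a steroid hold, or whether the table restart still applies after one.

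**Conclusion.** The point holds within limits. For Grade 2-3 diarrhea with onset in cycle 2 or later and Grade 2-3 renal toxicity, judged related to pembrolizumab and treated with systemic steroids and a taper as in Section 6.11, a hold that complies with the steroid bar cannot fit within 14 days. It exceeds 28 days, and reaches at least 42 if resolution takes 14 days, which is two to three times the stated maximum. A literal restart would overlap the taper, and for renal Grade 3 could precede it. No passage states which rule prevails.

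The result assumes that the taper starts on the day Grade 1 is reached and lasts the four-week minimum. The protocol gives no incidence of steroid-treated events, so the number of patients affected is unknown.

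A reader might infer that the safety run-in rule or the primary analysis is compromised. Neither follows. Section 8.2.1 counts patients requiring a BGB324 reduction or a permanent discontinuation, and both outcomes in these table rows (restart at 100 mg, or stop) count, so that section needs no change. The objective response rate analysis is unaffected. This is a conflict of wording with a safety bearing, not a flaw in the statistical design.

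**What to change.** Reconcile the BGB324 columns of Tables 15 and 17 with Sections 6.8 and 6.11 by adding a note under both tables. The note should state, for a patient whose event has resolved while systemic corticosteroids continue:

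- whether the restart instruction waits for completion of the steroids;
- whether the 14-day limit runs during that time;
- whether the table's restart instruction still applies after such a hold.

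For renal Grade 3, the note should also cover the restart at tolerable Grade 2. The sponsor sets the clinical rule; this review takes no position on it. The cost is amendment wording and a cross-reference, with no extra procedures or patients.
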